2. LIST OF ABBREVIATIONS

Term	Definition / description
ADA	Ati-drug antibody
AE	Adverse event
AESI	Adverse event of special interest
BMI	Body mass index
CTP	Clinical Trial Protocol
DBL	Dtabase lock
ICH	International Conference on Harmonisation
MedDRA	Medical Dictionary for Regulatory Activities
PKS	Pharmacokinetic set
PV	Potocol violation
RPM	Report planning meeting
RS	Randomised set
SAE	Serious adverse event
SD	Standard deviation
TS	Treated set
TSAP	Trial statistical analysis plan

3. INTRODUCTION

As per International Conference on Harmonisation (ICH) E9, the purpose of this document is to provide a more technical and detailed elaboration of the principal features of the analysis described in the protocol, and to include detailed procedures for executing the statistical analysis of the primary and secondary variables and other data.

This trial statistical analysis plan (TSAP) assumes familiarity with the Clinical Trial Protocol (CTP), including Protocol Amendments. In particular, the TSAP is based on the planned analysis specification as written in CTP Section 7 'Statistical Methods and Determination of Sample Size'. Therefore, TSAP readers may consult the CTP for more background information on the study, e.g., on study objectives, study design and population, treatments, definition of measurements and variables, planning of sample size, randomisation.

SAS® Version 9.4 (or later version) will be used for all analyses.

This initial version of the TSAP is defining important protocol violations in [Section 6.2](#).

4. CHANGES IN THE PLANNED ANALYSIS OF THE STUDY

There will be no changes in the planned analysis of the study.

5. ENDPOINT(S)

5.1 PRIMARY ENDPOINT(S)

CTP 5.2.1 defines the frequency [N(%)] of subjects with drug-related AEs as primary endpoint.

5.2 SECONDARY ENDPOINT(S)

5.2.1 Key secondary endpoint(s)

There are no key secondary endpoints in this trial.

5.2.2 Secondary endpoint(s)

CTP 5.5.1.1 defines the following pharmacokinetic parameters for BI 655130 as secondary endpoints:

IV administration:

- $AUC_{0-\infty}$ (area under the concentration-time curve of the analyte in plasma over the time interval from 0 extrapolated to infinity)
- C_{\max} (maximum measured concentration of the analyte in plasma)
- CL (total clearance of the analyte in the plasma after intravenous administration)
- V_{ss} (Volume of distribution at steady state after intravenous administration)

SC administration:

- $AUC_{0-\infty}$ (area under the concentration-time curve of the analyte in plasma over the time interval from 0 extrapolated to infinity)
- C_{\max} (maximum measured concentration of the analyte in plasma)

6. GENERAL ANALYSIS DEFINITIONS

6.1 TREATMENT(S)

For basic study information on investigational products, assignments of treatment, and selection of doses, please see CTP, Sections 3 and 4.

All subjects on active treatment will be analysed according to their actual treatment group. All placebo subjects will be analysed in one pooled placebo group (i.e. no distinction between dose groups will be made).

The following separate study phases will be defined for analyses of adverse events (AEs), laboratory tests, and vital signs:

- **Screening** (ranging from 0:00 h on day of informed consent until first administration of study drug)
- **On-treatment** (separately for each treatment, ranging from the time of first administration of the respective treatment until study termination date)

Displays of AEs, laboratory tests and vital signs will account for the treatments ([Table 6.1: 1](#)) during on-treatment phase.

A) High-level analysis (for CTR Section 15.3 and Appendix 16.1.9.2.8.2 displays)

In this analysis screening and post-study periods will not be included. In Section 15.3 AE tables (but not in Appendix 16.1.9.2.8.2 AE tables), the following totals will be provided in addition to the by treatment display:

- a total over all active treatments during on-treatment phase, excluding placebo ("Total BI")
- a total over the on-treatment phase and placebo ("Total")

B) Low-level analysis (for Appendix 16.1.9.2.8.1 displays)

Results will be presented separately for the following phases:

- Screening
- On-treatment (labelled with the name of the study drug administered at the start of the on treatment phase)

In Section 16.1.9.2.8.1 AE tables, the following totals will be provided in addition:

- a total over all active treatments during on-treatment phase, excluding placebo ("Total BI")
- a total over all phases ("Total")

Table 6.1: 1 Treatment Set-up

	Treatment	Short label
A	BI 655130, [REDACTED] iv	[REDACTED] iv
B	BI 655130, [REDACTED] iv	[REDACTED] iv
C	BI 655130, [REDACTED] iv	[REDACTED] iv
I	Placebo, iv	Placebo
D	BI 655130, [REDACTED] sc injection	[REDACTED] sc
S	Placebo, sc injection	Placebo

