3. DESCRIPTION OF DESIGN AND TRIAL POPULATION

3.1 OVERALL TRIAL DESIGN AND PLAN

The single rising intravenous dose part of the trial is designed as double-blind, randomised, and placebo-controlled within parallel dose groups. The single subcutaneous dose part of the trial is designed as double blind, randomised, and placebo-controlled.

A total of 32 healthy male subjects is planned to participate in the trial, according to 4 dose groups comprising 8 subjects per group. Within each dose group 6 subjects will receive the active drug and 2 subjects will receive placebo.

Only single dose is tested within each dose group. The dose groups to be evaluated are outlined in Table 3.1: 1 below.

Table 3.1: 1 Dose groups

Dose group	1	2	3	4
Dose	intravenous			subcutaneous
	[REDACTED]	[REDACTED]	[REDACTED]	[REDACTED]
No. of subjects	8	8	8	8
Subjects receiving placebo	2	2	2	2
Subjects receiving active	6	6	6	6

The dose groups will be investigated consecutively in ascending order of doses, maintaining a time interval of at least 14 days between the first drug administration in the previous dose group and the first drug administration of the subsequent dose group in single rising dose part. (Dose groups 1-3) The decision to proceed to the next dose group will be based upon the safety and tolerability data of the preceding dose groups. The next dose will only be given if, in the opinion of the investigator, no safety concerns arose in the preceding dose group (i.e. no dose-limiting events occurred) and if none of the pre-specified trial-specific stopping criteria were met (refer to [Section 3.3.4.2](#)).

The investigator is allowed to interrupt the further dose escalation in case the safety evaluation leads to concerns until alignment with sponsor.

An overview of all relevant trial activities is provided in the [Flow Chart](#). For visit schedules and details of trial procedures at selected visits, refer to [Sections 6.1](#) and [6.2](#), respectively.

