3.2 DISCUSSION OF TRIAL DESIGN, INCLUDING THE CHOICE OF CONTROL GROUPS

For single rising dose part, the design described in [Section 3.1](#) is viewed favourable under the provision not to expose the subjects involved to undue risks since the main study objective is to investigate safety and tolerability of BI 655130.

With the rising dose design, double-blind conditions regarding the subject's treatment (active or placebo) are maintained within each dose group. However, the current dose level will be known to subjects and investigators. The disadvantage of this trial design is a possible observer bias with regard to the dose-depending effects as well as time effects, but it has the virtue of minimizing subject risk by sequentially studying ascending doses. As time-effects are expected to be small relative to the differences between the doses in the broad range investigated, unbiased comparisons between treatments can still be expected.

The single subcutaneous part () will start at least 1 week after the first drug administration of the first dose group () of the single-rising intravenous dose part.

It is standard in trials involving healthy volunteers to include a placebo group as control for the evaluation of safety and tolerability. Each dose group consists of 8 subjects with 6 on active treatment, and 2 on placebo. The placebo control group includes all subjects of all dose

Proprietary confidential information © 2017 Boehringer Ingelheim International GmbH or one or more of its affiliated companies

groups treated with placebo. 6 subjects per active treatment group are in general considered as sufficient for the exploratory evaluation of pharmacokinetics.

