5.2 SAFETY

5.2.1 Endpoints of safety

Primary endpoint to assess safety and tolerability of BI 655130 is the number [N (%)] of subjects with drug-related AEs.

Further criteria of interest:

- AEs (including clinically relevant findings from the physical examination)
- Safety laboratory tests
- 12-lead ECG
- Continuous ECG monitoring
- Vital signs (blood pressure, pulse)

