7.3.3 Safety analyses

Safety will be assessed for the endpoints listed in [Section 5.2.1](#). All treated subjects (that is, all subjects who received at least one dose of study drug), will be included in the safety evaluation. Safety analyses will be descriptive in nature and will be based on BI standards. No hypothesis testing is planned.

Treatments will be compared in a descriptive way. The placebo control group in the safety evaluation will consist of all placebo treated subjects, regardless of the dose group in which they were treated. The active treatment groups will be compared to the placebo group in a descriptive way. Tabulations of frequencies/proportions will be used for the evaluation of categorical (qualitative) data, and tabulations of descriptive statistics will be used to analyse continuous (quantitative) data.

Measurements (such as vital signs, or laboratory parameters) or AEs will be assigned to treatments (see [Section 4.1](#)) based on the concept of treatment emergent AEs. Therefore, measurements planned or AEs recorded prior to first intake of trial medication will be assigned to 'screening', those between first trial medication intake until the end of trial visit will be assigned to the treatment period, and those after the end of trial examination will be assigned to 'post-study'. These assignments including the corresponding time intervals will be defined in detail in the TSAP.

Adverse events will be coded using the Medical Dictionary for Regulatory Activities (MedDRA). Frequency, intensity and causal relationship of AEs will be tabulated by treatment, primary system organ class and preferred term. SAEs, AESIs (see [Section 5.2.2.1](#)) and other significant AEs (according to ICH E3) will be listed separately.

Laboratory data will be compared to their reference ranges. Values outside the reference range will be highlighted in the listings. Additionally, differences from baseline will be evaluated.

Vital signs or other safety-relevant data observed at screening, baseline, during the course of the trial and at the end-of-trial examination will be assessed with regard to possible changes compared to findings before start of treatment.

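### The single pooled placebo column combines 6 IV and 2 SC placebo subjects, so every active-versus-placebo reading mixes drug with route: the SC column most, the IV columns less and in the opposite direction

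*SAP*

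**What the plan says.** Protocol 3.1 plans four groups of eight: "Within each dose group 6 subjects will receive the active drug and 2 subjects will receive placebo". Protocol 4.1.3 makes three of these groups intravenous and one subcutaneous.

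The placebo rule is the same wherever it appears. SAP 6.1: "All placebo subjects will be analysed in one pooled placebo group (i.e. no distinction between dose groups will be made". Protocol 7.3.3 says that the control group "will consist of all placebo treated subjects, regardless of the dose group in which they were treated" and compares each active group with it descriptively. Protocol 3.2 also pools placebo over all dose groups.

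SAP Table 6.1: 1 codes the two placebos separately, I for the infusion and S for "Placebo, sc injection", but gives both the short label 'Placebo'. The short labels of the active treatments carry their route. SAP 6.1 also plans a 'Total BI' column, "a total over all active treatments during on-treatment phase, excluding placebo".

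The result read against this column is the primary endpoint (Protocol 5.2.1): "Primary endpoint to assess safety and tolerability of BI 655130 is the number [N (%)] of subjects with drug-related AEs".

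**The concern.** Pooling placebo over dose levels of one route is ordinary practice in a rising-dose trial. This pool also crosses routes: a 90-minute infusion and an abdominal injection (Protocol 4.1.4). If adverse events on placebo differ by route, a difference between an active column and the pool is partly a route difference.

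The public text gives no reason for crossing routes. The design discussion in Protocol 3.2 deals with observer bias and time effects ("As time-effects are expected to be small relative to the differences between the doses in the broad range investigated"), not with the mode of administration.

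What is at stake is how a descriptive table is read. A pooled 2/8 (25%) may be 2/2 on SC placebo, 2/6 on IV placebo, or one of each. The headline row would not say which. Preferred terms for site reactions would partly reveal the route; general terms and the overall N (%) would not.

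**Working it through.** **Plan's own figure.** 4 x (6 + 2) = 32 subjects, as stated in Protocol 3.1.

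**Make-up of the columns.** Placebo: 3 x 2 = 6 IV and 1 x 2 = 2 SC, pool 8. Active: 3 x 6 = 18 IV and 6 SC. The share of the comparator that had the other route is 6/8 = 75% for the SC column and 2/8 = 25% for each IV column.

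**Shift with no drug effect.** Let p_iv and p_sc be the event rates by route.

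- Pool = (6 p_iv + 2 p_sc)/8
- SC minus pool = 0.75 x (p_sc - p_iv)
- Each IV column minus pool = -0.25 x (p_sc - p_iv)
- 'Total BI' minus pool = (18 p_iv + 6 p_sc)/24 - (6 p_iv + 2 p_sc)/8 = 0 at planned numbers

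The rates below are assumptions; neither document gives any.

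| p_iv | p_sc | SC minus pool (points) | Each IV minus pool (points) |
|---|---|---|---|
| 5% | 10% | +3.75 | -1.25 |
| 5% | 20% | +11.25 | -3.75 |
| 5% | 40% | +26.25 | -8.75 |
| 20% | 5% | -11.25 | +3.75 |
| equal | equal | 0 | 0 |

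**Shift against chance variation.** Exact binomial enumeration (active n=6, IV placebo n=6, SC placebo n=2), no drug effect. The result is the chance that the active column exceeds the pool by 20 points or more. The reference case gives both routes the active column's own rate. The 20-point mark is illustrative; with n=6 it needs at least 2 events, since 1/6 is 16.7%.

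| Column | p_iv, p_sc | Chance | Reference, no route gap |
|---|---|---|---|
| SC | 5%, 10% | 10.6% | 9.5% |
| SC | 5%, 20% | 30.7% | 20.5% |
| SC | 5%, 40% | 65.7% | 24.2% |
| SC | 20%, 5% | 2.1% | 3.1% |
| IV | 5%, 20% | 2.8% | 3.1% |
| IV | 20%, 5% | 24.0% | 20.5% |

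Much of the 30.7% is small-sample noise, and a 5-point route gap adds almost nothing.

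**Observation by route.** Footnote 5 in the flow charts marks the local tolerability test. After dosing, the IV chart has it at 1:30, 4, 12 and 24 h (4 times). The SC chart has it at 0:30, 4, 12, 24, 34, 48, 72, 96, 168, 336, 504, 672, 840, 1008 and 1344 h and at EOT (16 times). So 75% of the SC column's comparator follows the shorter schedule.

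**Could SC placebo replace the pool?** Exact 95% upper limits with no events: 0/2 84.2%, 0/6 45.9%, 0/8 36.9%. At 5%, 20% with no drug effect, SC minus pool has bias 11.25 and SD 19.0 points, so root-mean-square error sqrt(11.25^2 + 19.0^2) = 22.1 points. SC minus SC placebo is unbiased but has error 32.7 points. At 5%, 40% the errors are 34.8 and 40.0 points. The pool has the smaller error in both cases.

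**The case against.** The pooling is a declared choice, stated consistently in both documents, and the shared short label follows from it. Protocol 7.2 rules out confirmatory tests and Protocol 7.6 bases the sample size on no power calculation. No document shows that placebo event rates differ by route, and large distortions need large assumed gaps. A two-subject column can read only 0, 50 or 100% and cannot separate drug from route.

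All of this stands. It limits the point to how the tables are displayed and read, and it is why the pool should remain the comparator. It does not remove the gap: in a descriptive trial the table is the evidence, and one pooled count hides where the placebo events arose.

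Three stronger readings are tempting.

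- A reader might infer that only the SC column is affected. All four active groups are read against the same pool, and the IV shift is a third as large with the opposite sign. If p_sc exceeds p_iv, it could mask an IV excess.
- A reader might infer that the documents never justify the pooling or never show route. Some background sections named in the amendment log are absent from the public text, AE summarisation partly defers to a sponsor document, and SAP 6.1 keeps separate codes and plans low-level displays labelled by study drug. The claim can cover only the visible text and the planned pooled column.
- A reader might infer from the flow charts that SC placebo will show more drug-related AEs. They show unequal opportunity to record local findings, not unequal rates.

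**Conclusion.** The point holds as a low-severity matter of display. At planned numbers, 75% of the SC column's comparator and 25% of each IV column's comparator had the other route. The shifts are 0.75 x (p_sc - p_iv) for SC and -0.25 x (p_sc - p_iv) for each IV column; 'Total BI' is balanced. Their size and sign rest wholly on event rates that the documents do not give, and they are zero if the rates are equal. The different local-check schedules are a documented reason not to take equality for granted for local findings. The calculations assume planned numbers and no drug effect. No hypothesis test or error rate is affected, and the documents do not contradict each other here.

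**What to change.** Keep the pooled group as the planned comparator and leave the primary endpoint unchanged.

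1. In SAP Table 6.1: 1, label code I 'Placebo iv' and code S 'Placebo sc', and add a label 'Placebo total' for the pool.
2. Show 'Placebo iv' (n=6) and 'Placebo sc' (n=2) beside 'Placebo total' in the drug-related AE table (primary endpoint) and the other AE tables of SAP 7.8.1.
3. Add to SAP 6.1: 'Placebo total is the comparator for all active groups. The Placebo sc column is supplementary: it shows only where events occurred. With two subjects (0/2 has an exact 95% CI of 0-84%) it can neither replace the pool nor separate drug from route.'

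The cost is three labels, a short note and two extra table columns. The codes exist already and no new data are needed. The downside is that a reader may over-read the two-subject column; the note is there to limit that.

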6.2 IMPORTANT PROTOCOL VIOLATIONS

Data discrepancies and deviations from the CTP will be identified for all subjects in the database (i.e., treated subjects and subjects with serious AE (SAE) which the investigator considered related to the screening procedure). Consistency check listings (for identification of violations of time windows) and a list of protocol deviations (e.g. deviations in drug administration, in blood sampling times, etc.) will be provided to be discussed at the report planning meeting (RPM). At this meeting, it will be decided whether a discrepant data value can be used in analyses or whether it must be corrected in the clinical database.

Each protocol deviation must be assessed to determine whether it is an important protocol violation (PV). For definition of important PVs, and for the process of identification of these, refer to the Boehringer Ingelheim reference document 'Protocol Violation Handling Definitions' [\(1\)](#).

If any important PVs are identified, they are to be summarised into categories and will be captured in the RPM minutes via an accompanying Excel spreadsheet [\(2\)](#). The following table contains the categories which are considered to be important PVs in this trial. If the data show other important PVs, this table will be supplemented accordingly by the time of the RPM. If substantial numbers of PVs are reported at the RPM, a decision about summarising the PVs in a tabular format will be made. Otherwise, only a PV listing will be provided.

The following [Table 6.2: 1](#) gives the important PVs for this trial.

Table 6.2: 1 Important Protocol violations

Category	Description
/ Code	
A	Entrance criteria not met
A1	Inclusion criteria violated
A2	Exclusion criteria violated
B	Informed consent
B1	Informed consent not available
B2	Informed consent too late
C	Trial medication and randomisation
C1	Incorrect trial medication administered
C2	Randomisation not followed
C3	Non-compliance
C4	Medication code broken inappropriately
C5	Incorrect administration of trial medication
D	Concomitant medication
D1	Prohibited medication use
E	Missing data
E1	Certain violations of procedures used to measure primary or secondary data
F	Incorrect timing
F1	Certain violations of time schedule used to measure primary or secondary data.

6.3 SUBJECT SETS ANALYSED

- Randomised set (RS):

This subject set includes all randomised subjects, whether treated or not.

- Treated set (TS):

This set includes all subjects who were provided with study medication and were documented to have taken at least one dose.

Section 7.3.1 of the CTP:

Plasma concentration data and parameters of a subject will be included in the statistical PK analysis if they are not flagged for exclusion due to a protocol violation relevant to the evaluation of PK (to be decided no later than in the Report Planning Meeting) or due to PK non-evaluability (as revealed during data analysis, based on the criteria specified below).

Exclusion of a subject's data will be documented in the CTR.

Relevant protocol violation may be:

- *Incorrect trial medication administrated, i.e. the subject received at least one dose of trial medication the subject was not assigned to*
- *Incorrect dose of trial medication administrated*
- *Use of restricted medications.*

Plasma concentrations and/or parameters of a subject will be considered as non-evaluatable, if for example

- *Missing samples/concentration data at important phases of PK disposition curve.*

The PK parameter analysis set (PKS) includes all subjects in the treated set who provide at least one PK parameter that was not excluded according to the description above.

- Pharmacokinetic set (PKS):

The PKS includes all subjects in the treated subjects who provide at least one PK parameter that was not excluded according to the description above.

The discussion of all exceptional cases and problems and the decisions on the allocation of subjects to populations will be made at latest at the RPM.

The following table summarises which subject sets will be used for the different analyses.

Table 6.3: 1 Subject sets analysed

Class of endpoint	RS	TS	PKS
Disposition, exposure	X		
Important PVs	X		
Primary endpoints		X	
Secondary endpoints and further parameters of interest in PK analyses			X
Safety endpoints		X	
Demographic/baseline endpoints		X	

6.5 POOLING OF CENTRES

This section is not applicable, because the study was performed in only one centre.

6.6 HANDLING OF MISSING DATA AND OUTLIERS

Data of screened subjects, who discontinued from the trial due to screening failures prior to administration of any trial medication, will not be included in the CTR except for those with SAEs which the investigator considered related to the screening procedures. The safety data of treated subjects who were withdrawn from the trial prematurely will be reported as far as available. All withdrawals will be documented and the reason for withdrawal recorded.

Handling of missing data is according to the CTP, Section 7.4. Additionally, handling information of missing data is shown as follows:

- Missing data and outliers of PK data are handled according to [\(3\)](#).
- Missing or incomplete AE dates are imputed according to BI standards (see 'Handling of missing and incomplete AE dates'). [\(5\)](#)

